13.4.5 Descriptive Analyses

Summary descriptive statistics for baseline and demographic characteristics, disposition, and medication use will be provided for the safety and vaccinated populations. These data will be presented in the following manner:

- Continuous data (e.g., age, weight, and height) will be summarized by mean, standard deviation, median, and range.
- Categorical data (e.g., sex and race) will be presented as counts and percentages.

All medications taken by or administered to study participants beginning 30 days before the Screening Visit and continuing throughout the study will be collected. All medications used will be coded according to the World Health Organization (WHO) drug dictionary. The number and percentage of participants receiving prior and concomitant medications/therapies will be presented overall and by medication class.

13.5 Interim Analysis

13.5.1 Interim Analysis of Efficacy Data

No interim analysis of efficacy data is planned for the study.

13.5.2 Interim Analysis of Safety Data

No interim analysis of safety data is planned for the study. Routine reviews by the NIAID DSMB will be conducted as planned in Section 12.8.2 DSMB Review.

13.5.3 Futility Analysis

No early stopping for futility is planned for this study.

13.6 Statistical Hypotheses

The set of null hypotheses are that the true probability of a protective antibody response, π , is ≤ 0.25 in a given subpopulation, representing an inadequate improvement in anti-COVID-19 Antibody Response after administration of

an additional vaccine dose to warrant further investigation in that subpopulation. This will be tested within each arm indexed by cohort and age group (i), additional vaccine dose (j), and IS treatment plan (k)

$$H_{0,(i,j,k)}: \pi_{(i,j,k)} \leq 0.25$$

The set of alternative hypotheses are that the true vaccine response rate, π , is >0.25 and may warrant further investigation in that subpopulation

$$H_{1,(i,j,k)}: \pi_{(i,j,k)} > 0.25$$

13.7 Sample Size Considerations

Early reports show that a significant number of individuals taking IS medications respond poorly or not at all to COVID-19 vaccination. Ruddy et al. reported 26% of chronic inflammatory rheumatic disease patients had undetectable SARS-CoV-2 antibody response after their first mRNA vaccine dose, but many seroconverted with the second dose such that only 6% had persistent undetectable SARS-CoV-2 RBD antibodies [16]. However, those taking MMF or rituximab were at much higher risk of not mounting a detectable antibody response (89% and 67%, respectively)[17]. Another report has demonstrated diminished overall serologic response in adults with chronic inflammatory diseases, particularly in those treated with B-cell depletion or antimetabolites including MTX, with a 50-fold and 3-fold reduction in post-vaccine antibody titers relative to immunocompetent controls[80].

Based on the emerging evidence in individuals taking IS medications, an ineffective rate of achieving a protective immune response after the additional vaccine dose was defined to be less than or equal to 0.25 (null hypothesis). The study is powered to reject the null hypothesis in each arm when the true response rate is 0.5 or greater as preliminary evidence the additional vaccine dose is effective in specific study population.

The proportion of participants in each arm (cohort, additional vaccine dose, and IS treatment plan group) to receive an additional vaccine dose and achieve a protective antibody response at Week 4 will be evaluated using a one-sided exact test with alpha = 0.05 to test against a null hypothesis that the true response rate is ≤ 0.25 . A sample size of 33 evaluable participants achieves at least 90% power to reject null hypothesis when the true response rate is 0.5 or greater.

Secondary analyses will compare the rate of achieving a protective immune response across arms using the multivariable logistic regression model. For comparisons of single arms, 33 evaluable participants per arm will provide 80% power to detect an odds ratio of 4.2 when the null hypothesis is true in one arm (improvement from 0.25 to 0.584). For comparisons that combine arms, pooling 3 arms (e.g., type of additional vaccine dose) will provide 80% power to detect an odds ratio of 2.3 (improvement to 0.394).

In order to account for up to 20% dropout within a given arm of participants missing Week 4 anti-COVID-19 antibody response data without a documented COVID infection, 40 participants within each subgroup defined by the Roche Elecsys® Anti-SARS-CoV-2 S assay. In each arm, the number of participants with Roche Elecsys® Anti-SARS-CoV-2 S results ≤ 200 U/mL will be capped at 40 participants, and the number of participants with Roche Elecsys® Anti-SARS-CoV-2 S results > 200 U/mL and ≤ 2500 U/mL will be capped at 40 participants.

An adaptive design will be employed such that cohorts may be added or modified in light of emerging evidence on autoimmune disease vaccination or of the development and authorization of COVID-19 vaccines.

14. Identification and Access to Source Data

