13.4.4 Analyses of Secondary and Other Endpoint(s)

For Stage 1, the multivariable logistic and linear regression models defined in Section 13.4.3 Supportive Analyses of the Primary Endpoint above will be used to compare response to additional homologous doses of COVID-19 vaccine for a variety of subgroups. Appropriate contrasts will be defined to compare vaccine response for the following:

- Continuing versus withholding IS medications will be compared within cohort (cohorts A and B only) and within and across type of vaccine.
- The types of additional vaccine dose administered will be compared within cohorts and across cohorts, and within and across IS treatment plan groups.
- Type of IS medications will be compared within and across each type of vaccine.
- Age groups and type of disease will be compared within and across each type of vaccine.
- Corticosteroid dose at baseline will be added as a covariate to the model to assess impact on vaccine response.
- Immune response to the initial COVID-19 vaccine regimen will be assessed within and across each type of vaccine.
- Additional covariates for disease activity, co-morbid illness, age, and sex may be added to assess whether the clinical parameters are associated with response to additional vaccine dose.

Data for the Moderna COVID-19 Vaccine and Pfizer-BioNTech COVID-19 Vaccine may be combined in the comparisons above to assess the effect of mRNA vaccines together.

The incidence of seroconversion following additional vaccine doses of COVID-19 vaccine will be evaluated in the subgroups of participants that are anti-COVID-19 antibody negative at baseline using separately, (a) NIAID-VRC MSD 3 plex (Wu-1 full-length spike, RBD, and N proteins) assay with thresholds <1204.7 , 517.9 , and 9779.6 AU/mL, respectively, and (b) the Roche Elecsys® Anti-SARS-CoV-2 S electrochemiluminescence immunoassay with a threshold <0.80 U/mL. The proportions who seroconvert within and across arms will be summarized using 95% Clopper-Pearson confidence intervals, and comparisons will use a two-sample Binomial exact test with nominal two-sided alpha = 0.05.

For the subgroups of participants that are anti-COVID-19 antibody positive at baseline using separately, (a) the NIAID-VRC MSD 3 plex (Wu-1 full-length spike, RBD, and N proteins) assay, and (b) the Roche Elecsys® Anti-SARS-CoV-2 S electrochemiluminescence immunoassay with a threshold ≥ 0.80 U/mL. Fold improvement for each assay will be defined as:

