8.1.4. Multiple Comparisons/Multiplicity

The primary analysis will be evaluated independently within each arm, and p-values will not be adjusted for multiple comparisons.

All secondary analyses will be conducted in an exploratory fashion, with any p-values and confidence intervals presented as descriptive statistics with no adjustments for multiple comparisons.

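### Protocol 13.7, pooled-arm power: from 0.25, an odds ratio of 2.3 is a response rate of about 0.434; the printed 0.394 is an odds ratio of 1.95

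*Protocol*

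**What the plan says.** Protocol 13.7 makes two power statements for secondary comparisons between arms.

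- Single arms: "For comparisons of single arms, 33 evaluable participants per arm will provide 80% power to detect an odds ratio of 4.2", with the rates given as "when the null hypothesis is true in one arm (improvement from 0.25 to 0.584".
- Pooled arms, in the next sentence: "pooling 3 arms (e.g., type of additional vaccine dose) will provide 80% power to detect an odds ratio of 2.3 (improvement to 0.394". Only the end rate is printed, so the starting rate carries over.

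The starting rate is 0.25 throughout. Section 13.6 tests against it, and 13.7 explains that "an ineffective rate of achieving a protective immune response after the additional vaccine dose was defined to be less than or equal to 0.25". No other reference rate appears in either section.

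Neither statement gives an alpha level or sidedness. The nearest stated convention is in 13.4.4, for seroconversion, where "comparisons will use a two-sample Binomial exact test with nominal two-sided alpha = 0.05". The SAP text provided has no sample-size section that restates or corrects these figures. On the status of the comparisons, SAP 8.1.4 says "All secondary analyses will be conducted in an exploratory fashion".

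**The concern.** Once the reference rate is fixed, an odds ratio and an end rate are the same quantity on two scales, so each determines the other. The single-arm pair converts correctly. The pooled pair, one sentence later, does not.

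The two readings differ materially. The bracketed rate implies that 14 points (0.394 − 0.25 = 0.144) can be detected with 80% power. The odds ratio implies about 18 points (0.434 − 0.25 = 0.184). The sentence's own example is vaccine type, and whether response differs by vaccine type is a listed secondary objective. A reader who trusts the bracket would expect the pooled comparison to be more sensitive than it is, and could over-read a null result.

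**Working it through.** **Inputs**

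- Reference rate 0.25; single-arm pair 4.2 and 0.584; pooled pair 2.3 and 0.394; 33 evaluable per arm; 80% power (all Protocol 13.7).
- Three pooled arms: 3 × 33 = 99 per group.
- Two-sided alpha 0.05: an assumption, tested in step 2.

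**Step 1. Odds ratio against rate (no power assumption needed)**

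OR = [p2/(1 − p2)] / [p1/(1 − p1)], with p1 = 0.25, so the reference odds are 0.25/0.75 = 0.333.

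- Single-arm pair: (0.584/0.416)/0.333 = 4.21, printed as 4.2. Consistent.
- Pooled odds ratio to rate: 2.3 × 0.333 = 0.767; 0.767/1.767 = **0.434**.
- Pooled rate to odds ratio: (0.394/0.606)/0.333 = **1.95**.
- Rounding: odds ratios from 2.25 to 2.35 give 0.429 to 0.439, so 0.394 is out of reach.
- Reference rate that would reconcile the pair: 0.650/2.3 = 0.283 odds, a rate of 0.220. Section 13.7 does not use it.

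**Step 2. Reproduce the plan's single-arm power**

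Normal approximation with pooled variance, n per group, p̄ the mean of the two rates:

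power = Φ{ [√n · (p2 − p1) − z · √(2p̄(1 − p̄))] / √(p1(1 − p1) + p2(1 − p2)) }

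With n = 33, 0.25 against 0.584 and z = 1.96: (1.919 − 1.367)/0.656 = 0.841, so power is **80.0%**, as stated. One-sided 0.05 would give 88.0%. Two-sided 0.05 is therefore the convention that matches the plan's own figure.

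**Step 3. The same formula for pooled arms**

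| Evaluable per group | Power at 0.394 | Rate detectable at 80% (odds ratio) |
|---|---|---|
| 99 (3 arms of 33) | 58.4% | 0.438 (2.34) |
| 144 (3 arms of 48: 60 less 20%, Adult Stage 1) | 74.6% | 0.404 (2.04) |
| 192 (3 arms of 64: 80 less 20%, other stages) | 85.8% | 0.383 (1.86) |
| 165 (5 arms of 33) | 80.2% | 0.394 (1.95) |

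For 99 per group and 0.394: (1.433 − 1.295)/0.653 = 0.211, which gives 58.4%. At 0.434, 99 per group gives 78.3%.

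The group size needed for 80% power is 104 at 0.434 and 165 at 0.394.

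**Step 4. Sensitivity to the test, 99 per group**

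| Method | 0.394 | 0.434 |
|---|---|---|
| Chi-square, exact enumeration | 58.8% | 78.5% |
| Wald test of log odds ratio | 57.7% | 77.1% |
| Fisher exact, two-sided | 53.0% | 74.0% |
| Pooled normal, one-sided 0.05 | 70.2% | 86.5% |

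No variant brings 0.394 to 80% with three arms of 33.

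**The case against.** The strongest counter-argument is that the wrong figure may be the number of arms. With five arms of 33 (165 per group) the rate detectable at 80% power is 0.3936, an odds ratio of 1.95, which is the printed 0.394. Five arms per vaccine is the Stage 1 layout: Table 2 lists A1, A4, B1, B4 and C1 for Moderna, and Table 7 has the same pattern for children. Pooling by vaccine in Stage 1 would then combine five arms, and the sentence may pair a three-arm odds ratio with a five-arm rate. On that basis 14 points does have 80% power.

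The arithmetic is right and the explanation is plausible, but it is an inference about origin. The sentence says three arms, and that count agrees with its odds ratio. In Stage 2, pooling by vaccine does give three arms (Tables 5 and 9). On either reading the printed trio of three arms, 2.3 and 0.394 is inconsistent.

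Two smaller points. The reference rate and alpha are inferred, not printed in the pooled sentence; but 0.25 is the only reference rate available, and two-sided 0.05 reproduces the preceding 80%. The logistic model is adjusted for covariates, so its odds ratio need not equal a ratio of crude odds; but the preceding sentence converts directly between crude rates and an odds ratio, so the same standard applies here.

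**Conclusion.** The concern holds. The mismatch in step 1 rests only on the reference rate of 0.25 and is not a rounding effect. The power figures also assume two-sided 0.05, equal groups and 33 evaluable per arm. On that basis a true improvement to 0.394 has about 58% power with three pooled arms, not 80%, and the difference detectable with 80% power is 18 to 19 points, not 14. The 58% does not carry over to other group sizes: with full arms less 20% dropout it becomes 74.6% or 85.8%, though neither basis yields the printed pair.

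This is a minor point. The sentence concerns secondary comparisons, which are exploratory and unadjusted. The primary single-arm test and its sample size (33 evaluable, 40 enrolled per subgroup) do not depend on it.

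**What to change.** Correct the pooled sentence in Protocol 13.7 so that the number of arms, group size, odds ratio and rate agree, and state the alpha level.

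- If three arms are meant: 99 evaluable per group, two-sided alpha 0.05, about 80% power for an odds ratio of 2.3, from 0.25 to about 0.434 (0.438, odds ratio 2.34, for exactly 80%).
- If 0.394 is the intended target: odds ratio 1.95, with about 165 evaluable per group, which is five arms of 33.

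The cost is a text edit. It needs no additional participants and changes no analysis. On the three-arm basis the stated detectable difference grows from 14 to about 18 points.

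### Forty participants per Elecsys subgroup, less the full 20% loss the protocol allows, leaves 32 evaluable rather than 33, with 89.2% power in that subgroup

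*Protocol*

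**What the plan says.** Protocol Section 13.7 describes the primary test as "evaluated using a one-sided exact test with alpha = 0.05", with a null response rate of 0.25, and powers it "when the true response rate is 0.5 or greater as preliminary evidence". The figure given is: "A sample size of 33 evaluable participants achieves at least 90% power to reject null hypothesis".

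The same section then moves from evaluable to enrolled numbers. The purpose is stated as "In order to account for up to 20% dropout within a given arm", where the dropouts meant are "participants missing Week 4 anti-COVID-19 antibody response data without a documented COVID infection". The resulting number is "40 participants within each subgroup defined by the Roche Elecsys" assay. The subgroups named are results up to 200 U/mL, and results above 200 and up to 2500 U/mL. Each "will be capped at 40 participants".

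Three other places bear on the point:

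- Protocol Section 13.4.2 runs the primary test within each arm and also within each of these subgroups. Participants whose Week 4 result is missing but who have a documented infection stay in as non-responders. Other missing results are treated as missing completely at random.
- Protocol Section 11.3 does not replace participants who withdraw after vaccination. Those never vaccinated do not count toward accrual and are made up by further enrolment.
- SAP Section 8.2.2 specifies the same exact test against 0.25.

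**The concern.** The 40 per subgroup is offered as the number that protects the sample size against up to 20% loss. A reader will take it that 33 evaluable, and so at least 90% power, survives that loss in each subgroup. It does not: one fifth of 40 is 8, which leaves 32.

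The gap cannot close in practice. The cap prevents over-enrolment, and losses after vaccination are not replaced. At stake is the accuracy of the planning figure for the subgroup tests. The validity of the test and its Type I error are not affected.

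**Working it through.** **Inputs** (Protocol Section 13.7): one-sided exact binomial test, alpha 0.05; null rate 0.25; alternative 0.50; 33 evaluable; 40 enrolled per subgroup; loss up to 20%.

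**Formula.** For n evaluable, the critical value r is the smallest count with P(X >= r | n, 0.25) <= 0.05. Power is P(X >= r | n, 0.50). Each probability is the sum over k = r to n of C(n,k) p^k (1-p)^(n-k).

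**The plan's own figure.** At n = 33, r = 13, the attained size is 4.84% and power is 91.9%. The statement of at least 90% at 33 evaluable reproduces.

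**The dropout step.** 40 x 0.80 = 32. Working back from the target, 33 / 0.80 = 41.25, which rounds up to 42. The 40 does match 33 x 1.20 = 39.6 rounded up, that is, adding 20% rather than dividing by 0.80. The protocol does not show the step, so that origin is an inference.

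**Power across the whole allowance, 40 enrolled:**

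| Lost | Loss | Evaluable | Critical value | Size | Power at 0.50 |
|---|---|---|---|---|---|
| 0 | 0% | 40 | 16 | 2.6% | 92.3% |
| 1 | 2.5% | 39 | 15 | 4.4% | 94.6% |
| 2 | 5% | 38 | 15 | 3.5% | 92.8% |
| 3 | 7.5% | 37 | 15 | 2.7% | 90.6% |
| 4 | 10% | 36 | 14 | 4.6% | 93.4% |
| 5 | 12.5% | 35 | 14 | 3.6% | 91.2% |
| 6 | 15% | 34 | 14 | 2.8% | 88.5% |
| 7 | 17.5% | 33 | 13 | 4.8% | 91.9% |
| 8 | 20% | 32 | 13 | 3.8% | 89.2% |

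Power is below 90% at two of the nine possible counts, 32 and 34. The lowest value is 88.5%.

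**Whole arms after 20% loss:**

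- 80 enrolled (Adult Stage 2, Pediatric Stages 1 and 2): 80 x 0.80 = 64 evaluable, r = 23, power 99.2%.
- 60 enrolled (Adult Stage 1): 60 x 0.80 = 48 evaluable, r = 18, power 97.0%.

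**The case against.** The strongest reply is that nothing in Section 13.7 is false as written. The power sentence refers to 33 evaluable and is right. No power is claimed for 32 evaluable or for 40 enrolled. The 20% is a ceiling, and it covers only missing Week 4 results without a documented infection, so the relevant loss runs over the few weeks from vaccination to the Week 4 visit. If 7 or fewer of 40 are lost, at least 33 remain. A move across 90% caused by one participant reflects the discreteness of the exact test.

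Most of this stands, and it limits the point to a small one. It does not remove it. The protocol itself chose 20% as the loss to be covered and 40 as the number that covers it, and 40 does not return 33 at that loss. Nor does keeping at least 33 secure 90%, since 34 gives 88.5%.

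Two stronger readings are tempting, and the documents support neither:

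- A reader might infer that the stated power of at least 90% is really 89.2%. The protocol attaches its figure to 33 evaluable, where exact power is 91.9%. The 89.2% arises only if a subgroup fills to 40 and loses the full 20%.
- A reader might infer that every arm falls short. The 40 is a subgroup number. Filled arms of 60 or 80 stay at 97.0% and 99.2% after 20% loss. Adult Stage 1, now closed, also used different strata (up to 50, and above 50 to 200 U/mL) within a total of 60, so both could not reach 40.

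**Conclusion.** The dropout step in Section 13.7 and its target of 33 evaluable disagree by one participant. At the full stated loss, a filled subgroup has 32 evaluable and 89.2% power. The lowest power anywhere within the allowance is 88.5%, at 34 evaluable. The shortfall against 90% is therefore 0.8 to 1.5 points where it occurs. This is a minor inaccuracy in a planning statement and does not make the design underpowered.

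The figures assume a subgroup that fills to 40, a true response rate of exactly 0.50 after documented infections with missing data are counted as non-responders, and the exact test at one-sided 0.05 as specified. A subgroup that does not fill would have fewer evaluable participants for reasons unrelated to this point.

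**What to change.** Keep 40 per subgroup and the cap, and restate the figure in Protocol Section 13.7. For example: *40 participants per subgroup with up to 20% loss leaves at least 32 evaluable, giving at least 88% power (89.2% at 32, 88.5% at 34) for a true response rate of 0.5.*

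Two alternatives are less good. Saying that 40 tolerates 17.5% loss with 91.9% power would mislead, because a smaller loss of 15% gives 88.5%. Raising the subgroup to 42 would restore the count but not the power claim: 42 x 0.20 = 8.4, so at most 8 could be lost, and 42 - 8 = 34 evaluable again gives 88.5%.

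The cost is one sentence, with no added participants and no change to the test. The stated power becomes slightly less favourable.

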14.1 Source Data

Source documents and source data are considered to be the original documentation where participant information, visit consultations, examinations, and other information are recorded. Documentation of source data is necessary for the reconstruction, evaluation and validation of clinical findings, observations and other activities during a clinical trial.

The investigator should retain all documentation relating to the study (including but not limited to informed consent forms, source documentation, study vaccine records, eCRFs, and essential documents) for a period of at least 2 years

after the last marketing application approval or, if no application will be filed or if the application is not approved, 2 years following the discontinuation of the investigation.

If this requirement differs from any local regulations, the local regulations will take precedence unless the local retention policy is less than 2 years.

At study closure, the investigator must inform DAIT/NIAID, or the SACCC as designee, of the long-term storage location of the study's records and must inform DAIT/NIAID if that location changes subsequently.

No study records should be destroyed without prior authorization from DAIT/NIAID.

14.2 Access to Source Data

The site investigators and site staff will make all source data available to the DAIT/NIAID and authorized representatives of DAIT/NIAID, as well as to relevant health authorities. Authorized representatives as noted above are bound to maintain the strict confidentiality of medical and research information that may be linked to identified individuals.

15. Quality Assurance and Quality Control

The principal investigator (PI) is required to keep accurate records to ensure that the conduct of the study is fully documented. The PI is required to ensure that all eCRFs are completed for every participant entered in the trial. The period of record retention should be consistent with the record retention policies of the sponsoring agency or applicable regulatory agencies. However, in certain instances, documents should be retained for a longer period if required by the applicable regulatory agency or by the NIH.

Data will be obtained from a variety of sources including, but not limited to laboratory notebooks, automated instrument output files, and clinical participant charts. Data from these source materials will be transmitted to the SACCC via one of two mechanisms. Data collected electronically at central laboratories will be transferred electronically directly from the laboratory to the SACCC using standard secure data transfer procedures. Data collected at the clinical sites will be transmitted to the SACCC using an internet-based remote data entry system. Clinical site personnel use an internet browser to key data into eCRFs; each eCRF page is submitted to the clinical database electronically as the page is completed. Univariate data validation tests are performed as the data are keyed. The clinical database is backed up nightly; backup tapes are saved in a secure, off-site location. At any time, authorized site personnel may log in to the remote data entry system, review and correct previously entered data, or key additional data. The data will be further validated per the study data validation plan via a series of computerized and manual edit checks, and all relevant data queries will be raised and resolved on an ongoing basis. Complete, clean data will be frozen to prevent further inadvertent modifications. All discrepancies will be reviewed and any resulting queries will be resolved with the investigators and amended in the database. All elements of data entry (i.e., time, date, verbatim text, and the person performing the data entry) will be recorded in an electronic audit trail to allow all data changes in the database to be monitored and maintained in accordance with federal regulations.

The SACCC is responsible for regular inspection of the conduct of the trial, for verifying adherence to the protocol, and for confirming the completeness, consistency, and accuracy of all documented data.

The SACCC will periodically visit the participating clinical sites and audit the source documents in order to validate the data in the SACCC central database. If on-site visits are not permitted at a site due to COVID-19 restrictions, source document review and other visit activities will be conducted remotely. Data will be provided using the participant's identification number, the SACCC will not collect personally identifying information such as the participant's name or social security number. Participants will provide demographic information such as race, ethnicity, and birth date.

Data collected by the SACCC will be held in the strictest confidence, and are protected from access that could reveal personally identifying information about any participant in the trial.

16. Protocol Deviations

